10.4 Sample Size and Power Calculations

10.4.1 Primary Endpoints

The proposed total sample size is approximately N=96 adolescent females randomized to two arms in a 3:1 ratio giving 72 adolescent females in the dapivirine VR arm and 24

adolescent females in the placebo VR arm. The sample size is based upon the size of similar Phase 2a studies of vaginal microbicide products and includes a 3:1 ratio of drug to placebo arms to allow for the collection of additional safety endpoints in the drug arm while maintaining blinding between arms.

As a means to characterize the statistical properties of this study Table 13 presents the probability (expressed as a percent) of observing zero, at least one, and two or more safety endpoints among the 72 adolescent females in the dapivirine VR arm for various 'true' event rates.

Event Rate (%)	P (0 events n=72) (%)	P (> 1 event n=72) (%)	P (> 2 events n=72) (%)
0.5	69.7	30.3	5.1
1.0	48.5	51.5	16.2
3.5	7.7	92.3	72.2
5	2.5	97.5	88.1
10	0.05	99.95	99.5
15	0.0	99.99	99.99

An alternative way of describing the statistical properties of the study design is in terms of the true rate based on the observed data. Table 14 shows the exact 2-sided 95% confidence intervals for the probability of an event based on a particular observed rate. For example, if none of the 72 participants using the dapivirine VR experiences a safety event, the 95% exact 2-sided confidence interval for the true rate of event is (0.0%, 4.99%). If we see 2 events, this changes to (0.34%, 9.68%).

 Table 13: Exact Two-sided 95% Confidence Intervals Based on Observing a Particular Rate of Safety Endpoints for Arms of Size 72

Observed event rate, percentage (fraction)	Confidence interval (%)
0.0 (0/72)	(0.0, 4.99)
1.4 (1/72)	(0.04, 7.50)
2.8 (2/72)	(0.34, 9.68)

The primary aim of the study is to compare the safety between the two arms (dapivirine VR arm versus placebo VR arm). Assuming a two-sided Fisher's Exact test with α =.10 and 80% or 90% power, Table 15 provides the difference in the rates of safety events (proportion of females experiencing the safety event of interest) between the dapivirine VR arm and the placebo VR arm that is detectable for a given rate in the placebo VR arm. For example, if the true rate of a given toxicity endpoint in the placebo VR arm is 4.2% (1 out of 24 females experiencing a safety event); the proposed sample size provides 90% power to detect safety endpoint rates greater than 30.2% (26.3% with 80% power).

True Rate in Placebo Arm, percentage (fraction)	Observed Rate in Drug Arm Detectable with 80% Power, percentage (fraction)	Observed Rate in Drug Arm Detectable with 90% Power, percentage (fraction)
4.2 (1/24)	26.3 (19/72)	30.2 (22/72)
8.3 (2/24)	33.0 (24/72)	37.4 (27/72)
20.8 (5/24)	49.5 (36/72)	54.5 (39/72)
41.7 (10/24)	70.6 (51/72)	75.7 (55/72)
62.5 (15/24)	87.8 (63/72)	91.3 (66/72)

 Table 14: Difference in the Observed Rates of Safety Events

A lower retention rate, 75%, is also considered. Assuming non-differential loss to follow-up, the sample size is then N=72 adolescent females with 54 adolescent females randomized to the dapivirine VR arm and 18 adolescent females in the placebo VR arm. Table 16 presents the probability of observing zero, at least one, and two or more safety endpoints among the 54 adolescent females in the dapivirine VR arm for various 'true' event rates.

Table 15: Analysis of Safety Event Frequency

Event Rate (%)	P (0 events n=54) (%)	P (> 1 event n=54) (%)	P (> 2 events n=54) (%)
0.5	76.3	23.7	3.0
1.0	58.1	41.9	10.2
3.5	14.6	85.4	56.8
5	6.3	93.7	75.9
10	0.3	99.7	97.6
15	0.02	99.98	99.8

Table 17 lists the exact 2-sided 95% confidence intervals for the probability of an event based on a particular observed rate with 75% retention. For example, if none of the 54 participants using the dapivirine VR experiences a safety event, the 95% exact 2-sided confidence interval for the true rate of the event is (0.0%, 6.60%). If we observe 2 events, this changes to (0.45%, 12.74%).

Table 16: Exact Two-sided 95% Confidence Intervals Based on Observing a Particular Rate of
Safety Endpoints for Arms of Size 54

Observed event rate, percentage (fraction)	Confidence interval (%)
0.0 (0/54)	(0.0, 6.60)
1.9 (1/54)	(0.05, 9.89)
3.7 (2/54)	(0.45, 12.74)

Table 18 provides the difference in the rates of safety events between the dapivirine VR arm and the placebo VR arm that is detectable for a given rate in the placebo VR arm, assuming a two-sided Fisher's exact test with α =.10 and 80% or 90% power when retention is equal to 75%. For example, if the true rate of a given toxicity endpoint in the placebo VR arm is 5.6% (1 out of 18 females experiencing a safety event); the sample size N=72 provides 90% power to detect safety endpoint rates greater than 38.9% (33.3% with 80% power).

True Rate in Placebo Arm, percentage (fraction)	Observed Rate in Drug Arm Detectable with 80% Power, percentage (fraction)	Observed Rate in Drug Arm Detectable with 90% Power, percentage (fraction)
5.6 (1/18)	33.3 (18/54)	38.9 (21/54)
11.1 (2/18)	42.6 (23/54)	48.1 (26/54)
27.8 (5/18)	63.0 (34/54)	68.5 (37/54)
55.6 (10/18)	87.0 (47/54)	90.7 (49/54)
66.7 (12/18)	94.4 (51/54)	96.3 (52/54)

 Table 17: Difference in the Observed Rates of Safety Events for the Retention Rate of 75%

10.4.2 Secondary Endpoints

Acceptability Endpoint

Acceptability of the study VR (dapivirine or placebo) in sexually experienced, HIVnegative adolescent females for 24 weeks will be determined by participants rating several components of acceptability (e.g., discreetness, likes and dislikes concerning the ring, attitude toward product characteristics, comfort and ease of use, partner reactions, and effect on sex) on a combination of categorical and continuous scales.

Adherence Endpoint

Adherence will be measured by the percentage of women who keep the VR inserted at all times in the vagina over the course of 24 weeks. A sample size of 96 women will provide an absolute precision of 9.1% (i.e., half the width of the 95% confidence interval) assuming an observed adherence of 75%.

Pharmacokinetic Endpoint

The PK endpoint is a description of the end of period (28 day post ring insertion) plasma and vaginal fluid dapivirine concentrations at week 2, 4, 12 and 24, and will be descriptively compared to the same results in a recently studied population of adult women (MTN-013/IPM 026). Plasma and vaginal fluid will also be collected at Week 2. The 28 day assessment in each ring period represents near steady-state concentrations in prior dapivirine ring studies. The intent is to determine if the plasma and vaginal fluid dapivirine concentrations are different in adolescent females compared to adult females 28 days after insertion of dapivirine vaginal rings. The vaginal fluid will be collected in 96 females.

Approximately 36 women randomized to active ring will provide vaginal fluid swabs that will be weighed. From previous clinical trials with dapivirine Ring-004 (IPM 013 and IPM 024), the inter-participant CV% of vaginal fluid concentrations of dapivirine prior to ring removal on Day 28 ranged from 35% to 85%, depending on sampling location. If one assumes a CV% of 70%, and comparison of MTN-013/IPM 026 (N=12) to MTN-023/IPM 030 (N=36), then with 5% type I error and 80% power, we can exclude a difference as large as 0.95 SD units or a 67% difference.¹¹ These historical data for comparison are considered known and fixed. Approximately 36 women randomized to active ring will provide vaginal fluid swabs that will be not be weighed, given logistical constraints, however, these swabs will be analyzed for drug concentration without correction for weight. The variability of drug concentration from the unweighed swab cohort will be compared to the variability in the weighed swab cohort.

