Although these rings differ slightly from the IPM ring, the extensive clinical trial and postmarketing experience gained from these products provides further assurance of the safety of silicone elastomer rings as vaginal drug delivery devices. IPM recently evaluated the acceptability and safety of a similar placebo VR in the IPM 011 study (n=170). This study confirmed that the placebo ring was safe and acceptable to users and their male partners.

Pharmacokinetics

Vaginal fluid and blood for PK will be collected at follow-up visits. Tissue and intensive PK sampling have not been included in this safety study. In the event variations in drug levels between this adolescent population and an adult population are noted, additional studies may be considered.

MTN-023/IPM 030 will fill a void in the dapivirine VR research portfolio, providing the necessary safety data in sexually experienced adolescent females. These data will be added to the efficacy data anticipated from MTN-020 and IPM 027.

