10.8.3 Secondary Analyses

Acceptability

To assess acceptability of the study products, summary statistics will be calculated on each component of acceptability by arm.

Adherence

The average rate of VR use will be calculated in both arms along with 95% confidence intervals. These rates will be based on participant's self-report of product use at monthly clinic visits. The difference between adherence rates with its corresponding 95% confidence interval will be used to assess adherence of the study product compared to placebo.

Pharmacokinetics

A population mean and standard deviation of the end-of-period dapivirine concentrations for each woman in each 28-day period will be calculated based on the samples obtained as described above. The population mean from this study will be compared to the population mean and standard deviation from similar end of period dapivirine results for each matrix – plasma and vaginal fluid– in MTN-013/IPM 026, IPM 024, and IPM 013.

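### Protocol 10.4.2 says the PK comparison can exclude a 0.95 SD (67%) difference, but this is the difference it can detect with 80% power; exclusion in both directions is less likely

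*Protocol*

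**What the plan says.** Protocol 10.4.2 (Pharmacokinetic Endpoint) describes a descriptive comparison of end-of-period dapivirine concentrations with those of adult women in MTN-013/IPM 026. It gives the aim as follows: "The intent is to determine if the plasma and vaginal fluid dapivirine concentrations are different in adolescent females compared to adult females".

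For the roughly 36 active-ring participants whose vaginal swabs are weighed, it sets out a "comparison of MTN-013/IPM 026 (N=12) to MTN-023/IPM 030 (N=36"), assumes a CV of 70% from an earlier range of 35% to 85%, and concludes: "then with 5% type I error and 80% power, we can exclude a difference as large as 0.95 SD units or a 67% difference". The next sentence says that the historical data are treated as fixed and known.

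Protocol 10.8.3 gives the analysis: "The population mean from this study will be compared to the population mean and standard deviation from similar end of period dapivirine results", for plasma and vaginal fluid, against MTN-013/IPM 026, IPM 024 and IPM 013.

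Protocol 2.8.2 says what may follow: "In the event variations in drug levels between this adolescent population and an adult population are noted, additional studies may be considered".

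**The concern.** A detectable difference and an excluded difference are separate properties. Detection concerns how often a test is significant when the true difference has a given size. Exclusion concerns whether the interval for the difference, once observed, lies inside a bound. The sentence in 10.4.2 takes a detection figure and states it as exclusion. It gives no exclusion criterion, no direction and no assumed true difference, although the stated aim has two directions.

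Elsewhere section 10.4 keeps the two apart: the safety calculations are worded as power to detect, and adherence precision is given as a confidence-interval half-width. Only the PK sentence merges them.

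At stake is how a result without a visible adolescent-adult difference is described. A reader relying on 10.4.2 could credit the design with 80% assurance of ruling out a 67% difference in exposure among 15- to 17-year-olds. In both directions it does not have that assurance.

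**Working it through.** **Inputs (all from Protocol 10.4.2).** 12 adults; 36 adolescents with weighed swabs; "with 5% type I error and 80% power"; CV 70%, so 1 SD is 70% of the mean. Sidedness is not stated; two-sided reproduces the figure. The calculations assume normal data on the original scale, equal SDs and all 36 samples available.

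**Step 1. Reproduce the plan's figure.**
- SE = √(1/12 + 1/36) = √(4/36) = 0.333 SD.
- Normal approximation: (1.960 + 0.842) × 0.333 = 0.934 SD.
- Noncentral t, 46 df: detectable difference 0.954 SD; power at 0.95 SD is 79.7%.
- 0.95 × 70% = 66.5%, which rounds to 67%.
- One-sided 5% would give 0.84 SD, so the stated figure is the two-sided detectable difference.

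**Step 2. What a result must look like.** With t(0.975, 46) = 2.013, the 95% interval has half-width 2.013 × 0.333 = 0.671 SD (47% of the mean).
- Non-significant: observed difference below about 0.67 SD in absolute value.
- 95% interval inside ±0.95 SD: observed difference below about 0.95 − 0.671 = 0.279 SD.

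Observed differences between 0.28 and 0.67 SD are non-significant, yet do not exclude 0.95 SD.

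**Step 3. Probability of excluding 0.95 SD when the true difference is zero.**
Hand approximation, with SD taken as known after the half-width is set:
- One pre-chosen direction, 2.5% level: Φ(0.279/0.333) = Φ(0.837) ≈ 0.80.
- Both directions, 95% interval: 2 × Φ(0.837) − 1 ≈ 0.60.
- Both directions, two one-sided 5% tests (90% interval, half-width 1.679 × 0.333 = 0.560): 2 × Φ(0.390/0.333) − 1 = 2 × Φ(1.171) − 1 ≈ 0.76.

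Simulation of 1,000,000 trials with estimated SD:

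| Criterion | P(exclude 0.95 SD) | Bound excluded with 80% probability |
|---|---|---|
| One direction, upper limit of 95% interval | 80% | 0.95 SD (67%) |
| Both directions, two one-sided 5% tests | 76% | 0.99 SD (69%) |
| Both directions, 95% interval | 59% | 1.10 SD (77%) |

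Among non-significant results with zero true difference, the 95% interval still contains a 0.95 SD difference in one direction or the other in 37% of trials (20% with a 90% interval). With a true difference of 0.5 SD these become 64% and 46%.

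**Step 4. The fixed-data sentence.** If the adult mean were a known constant, the 12 adults would add no variance and the comparison would be one-sample with n = 36:
- SE = 1/√36 = 0.167 SD.
- Normal: 2.802 × 0.167 = 0.467 SD; t-based: 0.480 SD, or 0.480 × 70% ≈ 34%.
- With zero true difference, the 95% interval lies inside ±0.95 SD in over 99.9% of trials.

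The stated 0.95 SD therefore uses N = 12 as a source of variance, which the next sentence denies.

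**Sensitivity to CV.** Over the quoted range, 0.95 SD equals 0.95 × 35% = 33% to 0.95 × 85% = 81%.

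**The case against.** The case against is substantial, and most of it stands.

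- **The number is not miscalculated.** For one direction and zero true difference, detection and exclusion coincide at 80%. Under two one-sided tests at the stated 5%, the shortfall is small: 76% instead of 80%, or 69% instead of 67%. The larger gap (59%, 77%) appears only if a 95% interval must clear both sides, which is 2.5% per side. This stands and limits the size of the point.
- **The comparison is descriptive.** A reader might infer that a non-significant or un-noted difference will be reported as excluding 67%. The protocol does not say so. Section 2.8.2 is permissive and names no test.
- **It is not the only adult reference.** Section 10.8.3 also names IPM 024 and IPM 013, and covers plasma. The 12-versus-36 figure concerns one comparator and weighed vaginal swabs.
- **A reader might say that moderate differences would usually be missed.** That depends on size. A 35% difference (0.5 SD) is missed 69% of the time, but a 50% difference (0.71 SD) 45% of the time.
- **With fixed adult data, 0.95 SD is excluded almost always.** True, but the 0.95 SD figure was not derived that way. This exposes a conflict between two adjacent sentences; it does not rescue the claim.
- **Interval reporting is commonly left to the SAP.** Agreed: its absence from 10.8.3 is not counted as an error.

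What remains is that the sentence claims exclusion with 80% power without defining it, and that the two-sided aim does not have that property at 0.95 SD.

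**Conclusion.** The point holds as a minor correction. The 0.95 SD (67%) in 10.4.2 is a detectable difference, worded as an excludable one. With zero true difference, the stated 80% applies to exclusion in one pre-chosen direction; in both directions it is 76% or 59%, depending on the criterion. The protocol names neither criterion.

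The same passage also contradicts itself on the adult data: the figure takes the adult mean as estimated from 12 women, while the following sentence takes it as fixed, which would give about 0.48 SD (34%). The exclusion probabilities above hold only on the first reading and under the assumptions listed in the working.

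The documents do not support the stronger conclusion that the trial will declare adolescent and adult exposure similar from an absence of significance. No sample size, data collection or primary conclusion is affected.

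**What to change.** 1. **10.4.2, the precision sentence.** Either say that the comparison has 80% power to detect a difference of 0.95 SD (67% at CV 70%), or keep exclusion and state the criterion, the assumed true difference and the matching probability. For zero true difference, the bound excluded in both directions with 80% probability is about 0.99 SD (69%) with two one-sided 5% tests, or about 1.10 SD (77%) with a 95% interval.
2. **10.4.2, the next sentence.** Reconcile the fixed-data statement with the use of N = 12. Either drop it and keep the two-sample figures, or keep it, justify it and recompute on a one-sample basis (about 0.48 SD, 34%).
3. **10.8.3.** Report the adolescent-adult difference or ratio with its confidence interval for plasma and for vaginal fluid, and base any statement of similarity on the interval limits. If the SAP already does this, a cross-reference is enough.

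The cost is a few sentences and one interval per matrix and adult comparator. No added participants, samples or visits are needed. If exclusion in both directions is what is meant, the stated bound becomes somewhat less favourable.

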Data from post-use analysis of residual levels of dapivirine in Ring-004 (IPM 015, in which a ring was inserted once every 28 days over a 12-week period) indicate that, on average, 4 mg of dapivirine were released over approximately one month of ring use. The mean amounts of dapivirine remaining in the used rings were similar for Weeks 4, 8 and 12 (post-insertion), at 21.09 mg, 21.54 mg and 21.84 mg, respectively. No clear relationship (neither linear nor exponential) was observed between the residual amount of dapivirine and corresponding plasma concentrations (*i.e.* at scheduled ring removal). It would appear that plasma concentrations below approximately 200 pg/mL were generally associated with above-average ring residual amounts, while the residual amounts appeared relatively constant (at levels between approximately 20 and 22 mg) for plasma concentrations above this value (200 pg/mL).

Safety

Trial Details		Number of Participants					
Trial Number	Description	Country	Ring-001 reservoir (200 mg)	Ring-002 reservoir (25 mg)	Ring-003 matrix* (25 mg)	Ring-004 matrix** (25 mg)	Placebo Ring
IPM 001	Safety and PK in women; 7 days	Belgium	12				12 (crossover)
IPM 008	Safety and PK in women; 7 days	Belgium		10			3
IPM 013	Safety and PK in women; 56/57 days	Belgium				36	12
IPM 015	Safety and PK in women; 84 days	Multiple Countries in Sub- Saharan Africa		-		140	140
IPM 018	Safety and PK in women; 28 days	Belgium		8	8		8
IPM 024	Safety and PK in women; 28 days	Belgium				8	8

Table 1: Clinical Phase I/II Trials of Dapivirine Vaginal Rings

Trial Details			Number of Participants					
Trial Number	Description	Country	Ring-001 reservoir (200 mg)	Ring-002 reservoir (25 mg)	Ring-003 matrix* (25 mg)	Ring-004 matrix** (25 mg)	Placebo Ring	
MTN-013/ IPM 026***	Safety and PK in women	United States				12	12	
IPM 028	Drug-drug Interaction (miconazole nitrate); 28 days	Belgium				36	0	
IPM 034	Safety and PK in women; 7, 14, 28, 56, or 84 days	Belgium				40	0	
TOTAL participants		12	18	8	172	195		

*Tin-catalyzed matrix ring.

**Platinum-catalyzed matrix ring

*** MTN-013/ IPM 026 was the first in human clinical trial of a vaginal ring containing maraviroc alone, dapivirine alone or a combination of the two (dapivirine/maraviroc) compared to placebo. The dapivirine VR arm included 12 participants. It should be noted, however, that the dapivirine VR was similar to Ring-004, but of slightly different composition.

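### The stated 0.95 SD for the adult–adolescent PK comparison is a two-sample figure, which contradicts the next sentence treating the adult data as fixed and does not match the three-trial comparison in 10.8.3

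*Protocol*

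**What the plan says.** Section 10.4.2 (Pharmacokinetic Endpoint) describes the comparison with adult women as descriptive, but gives its purpose as determining whether adolescent and adult concentrations differ 28 days after ring insertion. It then attaches operating characteristics:

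- The adolescent sample: "Approximately 36 women randomized to active ring will provide vaginal fluid swabs that will be weighed".
- The contrast: "comparison of MTN-013/IPM 026 (N=12) to MTN-023/IPM 030 (N=36").
- The error rates: "then with 5% type I error and 80% power". Sidedness is not stated.
- The variability: "If one assumes a CV% of 70"%.
- The result: "we can exclude a difference as large as 0.95 SD units or a 67% difference".
- The next sentence: "These historical data for comparison are considered known and fixed".

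Section 10.8.3 (Pharmacokinetics) sets out the analysis: "The population mean from this study will be compared to the population mean and standard deviation from similar end of period dapivirine results", for plasma and vaginal fluid, in MTN-013/IPM 026, IPM 024 and IPM 013. It names no test. Section 2.6.1 says of the MTN-013/IPM 026 ring that "the dapivirine VR was similar to Ring-004, but of slightly different composition". Section 2.8.2 says further studies may be considered if drug levels in adolescents and adults are seen to vary.

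**The concern.** A detectable difference calculated from 12 and 36 women treats both means as estimates. Calling the adult data known and fixed treats one of them as a constant. These are different analyses with different standard errors, and the protocol puts one immediately after the other. An analyst who follows the fixed-data sentence would leave out the larger share of the variance, because the adult group is the smaller one. The result could be a difference between adolescents and adults declared on noise, in a setting where section 2.8.2 allows such a finding to prompt discussion of further studies.

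Two further points concern the same figure. It is sized against one adult trial, while 10.8.3 uses three. It is also described as a difference that can be excluded, although the calculation gives a difference that can be detected.

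**Working it through.** **Inputs.** From 10.4.2: 12 adults, 36 adolescents, 5% type I error, 80% power, CV 70%. From the table of ring trials in 2.6.1, active-ring women: MTN-013/IPM 026 12, IPM 024 8, IPM 013 36. Everything below is in SD units and assumes a common SD. Powers use the noncentral t distribution.

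**1. Reproducing the stated figure.** Two-sample, two-sided:

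- SE = √(1/12 + 1/36) = 0.333 SD, df = 46.
- Difference with 80% power: 0.954 SD. Power at 0.95 SD is 79.7%.
- In percent of the mean: 0.954 × 70% = 66.8%, the stated 67%.

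Other readings do not give 0.95: one-sided two-sample 0.84; one-sample with n = 12, 0.89; one-sample with n = 36, 0.48 (step 2); two-sample equivalence at 5%, 0.98 (normal approximation).

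**2. The same inputs with a fixed adult mean.** One-sample, n = 36:

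- SE = 1/√36 = 0.167 SD, df = 35.
- Difference with 80% power: 0.480 SD, and 0.480 × 70% = 34%.

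This is half the stated figure.

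**3. What is lost if the 12-woman mean is tested as a constant.**

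- Adult share of the variance of the difference: (1/12)/(1/12 + 1/36) = 75%.
- True SE over assumed SE: 0.333/0.167 = 2.
- With equal true means, a nominal two-sided 5% test rejects with probability 2·P(T₃₅ > 2.030/2) = 31.7%. The normal approximation gives 32.7%, and simulation (400,000 runs) 31.8%.

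**4. The comparison in 10.8.3.** If every active-ring woman in the three trials counts, there are 12 + 8 + 36 = 56 adults. Section 2.6.1 says, however, that only Group A of IPM 013 had its first ring removed on Day 28; Group B wore it to Day 35. If only Group A supplies comparable end-of-period values, and the groups were equal in size (18 active women), there are 12 + 8 + 18 = 38 adults.

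| Adults | SE (SD) | Detectable at 80% power | At CV 70% | Type I error if adult mean is taken as fixed |
|---|---|---|---|---|
| 12 | 0.333 | 0.95 SD | 67% | 31.7% |
| 38 | 0.233 | 0.66 SD | 46% | 15.5% |
| 56 | 0.214 | 0.60 SD | 42% | 12.2% |

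The last column uses 2·P(T₃₅ > 2.030/r), where r = SE/0.167. Pooling treats the three trials as one adult population, although one of them used a slightly different ring.

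**5. Exclude or detect.** Step 1 is a power calculation for a difference test, and a non-significant result from it would not rule out 0.95 SD. To exclude a difference with 80% power when the true difference is zero, the margin is about 0.98 SD (90% CI) to 1.08 SD (95% CI) by normal approximation, that is 68% to 76% at CV 70%.

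**The case against.** The best defence is that nothing is miscalculated: 0.95 SD and 67% follow from the stated inputs, and for 12 against 36 they are the sound figures. That stands. The fault is in the sentence beside them.

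Second, the protocol plans no one-sample test. Section 10.4.2 calls the comparison descriptive, and 10.8.3 brings forward the adult standard deviation as well as the mean, which a one-sample test would not need. A reader might infer that the trial will run a test with 32% type I error. The documents do not support that; the 32% describes what would follow if the sentence were applied literally. Nevertheless, 10.4.2 states an intent to determine whether concentrations differ and quotes type I error and power, so the descriptive label does not settle the matter.

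Third, *fixed* may mean only that the adult data are already collected and taken as reported. On that reading 0.95 SD stands, but the sentence adds nothing and still invites the wrong analysis.

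Fourth, sizing against the smallest comparator is conservative if more adults are added. That is true under a common SD, but the figure then does not describe the planned comparison.

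Fifth, the wording *exclude* matters little numerically: 0.98 SD against 0.95 SD on the 90% CI version. That is fair; it is a correction of meaning more than of size.

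The scale of analysis (log or original) and separate display of the different rings are matters a protocol commonly leaves to the SAP and are not part of this point.

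**Conclusion.** The point holds as an internal contradiction in 10.4.2 and a mismatch with 10.8.3. The stated 0.95 SD is correct for two samples of 12 and 36; a fixed adult mean would give 0.48 SD, so the figure and the fixed-data sentence cannot describe the same analysis. Taken literally, the sentence would lead to about 32% type I error with the 12 women of MTN-013/IPM 026, and about 12% to 15% with all three adult trials. These rates assume equal true means, equal SDs and a one-sample test that the protocol does not name. The range for three trials depends on how many IPM 013 women have comparable end-of-period data, and its lower adult count assumes equal groups.

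A reader might also infer that a false difference would set off new studies. Section 2.8.2 says only that they may be considered, and ties this to no significance test.

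The correction is moderate to minor. It concerns a secondary PK endpoint. The primary safety analysis is unaffected, and so is the trial's size, which 10.4.1 bases on similar Phase 2a studies.

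**What to change.** - In 10.4.2, delete the sentence that treats the historical data as known and fixed. State instead that the comparison carries the sampling error of the adult means, as a two-sample difference or ratio with a 95% confidence interval.
- Name the same adult trials in 10.4.2 and 10.8.3, say which IPM 013 women contribute, and restate the detectable difference for that set. If MTN-013/IPM 026 alone is kept, 0.95 SD (67%) stands.
- Replace *exclude* by *detect*, and state that the test is two-sided.

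The cost is a few words and at most one recalculated figure. The downside is a wider interval than a fixed-mean analysis would show: with 12 adults the standard error is twice as large.
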